Setmelanotide drug product (setmelanotide mPEG-DSPE formulation) is a sterile solution for injection. The product is manufactured at a concentration of 10.0 mg/mL.

Placebo is vehicle only and is identical in appearance to active treatment.

Setmelanotide and placebo will be administered as SC injection QD.

There will be extensive training of patients in drug administration including educational materials. Study-specific training materials will be provided to both the investigative staff and study participants and caregivers. Home nurses will be available, as needed, for additional training and to reinforce compliance. The Sponsor will provide extra placebo supplies for use during training.

Statistical Considerations

The primary statistical hypothesis is that the proportion of patients who are treated with setmelanotide for \sim 52 weeks who achieve \geq 10% reduction from baseline in body weight is greater than a historical control rate of 10% in the \geq 12 years old Full Analysis Set (\geq 12 yo FAS) (see definition in Section 8.2).

Data from the Clinical Registry Investigating Bardet-Biedl Syndrome (CRIBBS) were used to provide input for the sample size/power calculations. In particular, the natural history responder rate (percent of patients with weight loss ≥10% over a 1-year period) was assessed to determine the power estimates for the primary efficacy endpoint (see details in Section 8). The sample size is mainly driven by the primary hypothesis; although the rarity of the population is also taken into consideration.

Data from CRIBBS suggest that the proportion of subjects ≥ 12 years old who had $\geq 10\%$ spontaneous weight reduction from the previous 1-year period is approximately 6.4%. The power calculations assume a null historical control value of 10% who show at least a 10% weight loss, which is expected to be a conservative estimation. It is also expected that treatment with setmelanotide for ~ 52 weeks is associated with a true underlying probability of at least 66% who demonstrate at least 10% weight loss after ~ 52 weeks.

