3.4. Justification of the Study Design

Setmelanotide is being evaluated as a potential treatment for rare, genetically defined obese populations.

Both BBS and AS patients are included in the patient population of this study. While there is significant overlap in the clinical features of these syndromes, there are also some well known differences. However, despite any differences, the mechanism that drives the propensity for the obesity/hyperphagia phenotype is likely the same between the 2 syndromes, abnormal primary ciliary development and impaired leptin receptor signaling arising from BBSome dysfunction in

hypothalamic neurons caused by *BBS* or *ALM1* mutations. Because setmelanotide's mechanism of action in the MC4R pathway is downstream from the leptin receptor, it has the potential to be effective in both diseases.

Confirmation of efficacy will be based on weight loss response after ~52 weeks (1 year) of setmelanotide treatment compared to a historical weight loss rate taken from a large well characterized registry of BSS patients. The 1-year treatment duration was chosen to allow sufficient time for potential weight loss and to ensure that early weight loss is sustained. However, the study will also include a 14-week double-blind, placebo-controlled period in which 50% of patients will receive matching placebo and 50% will receive setmelanotide. Results from this placebo-controlled period will provide an insight into the immediate effect of setmelanotide compared with placebo on early weight loss and the unrelenting hunger/hyperphagia that is characteristic in these diseases. In particular, the effect of setmelanotide on hunger scores should be rapid and the evaluation strengthened by this initial placebo portion of the study. A full year double-blind, placebo-controlled period was not considered because the projected weight loss responder rate of the untreated population is well understood from the CRIBBS registry. Importantly, patient retention would be especially challenging in a full year placebo-controlled trial.

The rationale for using patients \geq 12 years of age at baseline for the primary efficacy analysis is provided in Section 8.5.1.

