8.5.2.1. Key Secondary Efficacy Analyses

Due to the rarity of the disease indication and small sample size, formal multiplicity adjustment procedures will be not enforced. However, to assist the comprehensive assessment and interpretation of the setmelanotide efficacy, appropriate statistical testing will be performed on the key secondary efficacy endpoints according the following hierarchical order to control the overall type I error rate. The p-values and the corresponding confidence intervals will be provided.

 The proportion of all patients, regardless of age at baseline, who achieve a ≥10% reduction from baseline in body weight (ie, are 'responders') after ~52 weeks of treatment with setmelanotide.

This is a similar endpoint to the primary endpoint but includes all patients, ie, regardless of age at baseline. The similar statistical method, analysis strategy and missing value handling approach that are described in Section 8.5.1 for the primary endpoint will be used. Additional supportive analyses on this endpoint based on Per-Protocol Analysis Set, the Stable Height FAS and the Active Growth FAS may be conducted as appropriate.

 Mean percent change from baseline in body weight (in patients ≥12 years of age at baseline) after ~52 weeks of treatment with setmelanotide.

 The proportion of patients who achieve a ≥25% improvement in the weekly average of the daily hunger score (in patients ≥12 years of age at baseline) after ~52 weeks of treatment with setmelanotide.

This binary endpoint will be analyzed using the similar statistical method, analysis strategy and missing value handling approach that are described in Section 8.5.1 for primary endpoint, based on the \geq 12 yo FAS.

 Mean percent change from baseline in the weekly average of the daily hunger score (in patients ≥12 years of age at baseline) after ~52 weeks of treatment with setmelanotide.

The continuous endpoint will be analyzed with a one-sample rank test, at a 1-sided 0.05 significance level, in the ≥12 yo FAS. The 2-sided 90% CI for the percent change from baseline will be provided. The similar analysis strategy and missing value handling approach that are described in Section 8.4 will be used while change from baseline will be imputed as 0 for treatment failures.

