3.7. Multiple Comparisons/Multiplicity

No multiplicity adjustments are required for the primary analysis as this study has only 1 primary endpoint. This controls the overall alpha at 0.025, 1-sided.

There are multiple key secondary efficacy endpoints planned in the study (see Section 1.3.5.1). However, based on the rarity of this disease, and the small number of patients to be enrolled in this study, the ability to use extremely rigorous statistical approaches to address multiplicity for these secondary endpoints is limited. Therefore, for publication, nominal-p-values will be used to interpret *each endpoint separately* in this small study. The Sponsor acknowledges that this approach may increase the probability of potential Type 1 error for the *set* of key secondary efficacy endpoints being analyzed. While this SAP does not envision multiplicity adjustments in this study, the Sponsor has pre-specified a step-down procedure (a hierarchical order of testing for the key secondary efficacy endpoints) to control Type-1 error, if needed for any purpose. The key secondary endpoints are presented according to the Sponsor-specified hierarchical order in Section 4.3.2.

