3.10.2. Approach on Missing Value Due to Other Reasons for ~52 Weeks Analysis

Every effort should be made to avoid missing values, but patients may have missing values due to other reasons such as lost to follow up, early dropout/discontinuation, missed visit, AEs etc. in addition to the administrative reason by the nature of the study design as described above. In these cases, the same principal and MI approach will be used for imputation of the missing value as outlined above. However, for the primary and key secondary analyses, these imputed values will then be replaced with the patient's baseline

value. This constitutes a treatment failure approach for these patients as the effective change and percent change from baseline will equate to 0. To assess the robustness of the analysis, a sensitivity analysis will also be conducted based on the imputed values themselves (no baseline replacement). For analyses outside of the primary and key secondary analyses, handling may differ based upon the analysis specified. Endpoints/analyses requiring imputations that are closely related to the primary or key secondary analyses will utilize the same handling as the primary and key secondary endpoints (baseline replacement). Other analyses utilizing imputation that are not closely related to the primary or key secondary analyses will utilize the values generated via multiple imputation and will not be replaced with baseline values. The specific handling for these analyses will also be outlined in the appropriate section below.

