4.3.1. Primary Efficacy Analysis

The primary efficacy analysis on the primary efficacy endpoint will be conducted in patients ≥12 years of age (at informed consent) in the FAS population.

[figure not shown]
The primary efficacy endpoint is the proportion of patients (≥ 12 years of age) who achieve a $\geq 10\%$ reduction in body weight from baseline after ~ 52 weeks of treatment. The null hypothesis (H0) to be tested is that the proportion of patients treated for ~ 52 weeks who achieve $\geq 10\%$ reduction in body weight from baseline is less than or equal to a historical control rate of 10%. The alternative hypothesis (H1) is that the proportion is greater than a historical control rate of 10%:

H0: $p_t \le 10\%$ vs H1: $p_t > 10\%$

where p_t is the response rate after ~52 weeks of treatment.

Please note that there are two different uses of "10%" above, which is explained here for clarity:

- The use of "10%" in the endpoint definition is the **response criteria** for an individual patient. If a patient achieves a ≥10% reduction from baseline in body weight, the patient will be categorized as a responder in this analysis. Otherwise, the patient will be categorized as a non-responder.
- The use of "10%" as the historical control **rate** is the historical reference/control response rate to be statistically compared to the observed response rate in patients treated with setmelanotide. The observed response **rate** of setmelanotide will be calculated with the number of responders (using the above 10% endpoint definition) divided by the number of total patients.

The primary endpoint will have binomial proportions calculated for each of the 100 imputed datasets. The outcomes from the 100 imputed datasets will be combined using Rubin's Rule to provide an overall estimate against the null hypothesis with corresponding confidence intervals and p-value (Little and Rubin, 2002). The 1-sided 0.025 significant level was chosen based on the small sample size due to the rarity of the disease. The success criterion for the primary hypothesis requires the rejection of the null hypothesis at the 1-sided 0.025 significance level. The statistical criterion corresponds to the 2-sided 95% CI for setmelanotide of the response rate excluding 10% (i.e., lower bound of the CI >0.10).

This analysis may be repeated on the following analysis sets: DUS, PP at EOP2, SH, AG, as appropriate.

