Descriptive statistics for the change and percent change from baseline in weekly average of daily hunger scores may be presented based on FAS population by active treatment visit.

Daily Hunger Score Reduction (Threshold of 25%) in Patients ≥ 12 Years of Age:

The proportion of patients in the FAS population who achieve a \geq 25% improvement from baseline in the weekly average of the daily hunger score after ~52 weeks of treatment will be analyzed similarly to the primary efficacy endpoint. Prior to analysis, daily hunger scores for each of the 3 hunger assessments will be averaged separately by week, as outlined above.

[figure not shown]
Descriptive statistics for the change and percent change from baseline in weekly average of daily hunger scores will be presented based on FAS population for analysis visits. Due to the

34

suitability of using the hunger score tool in younger patients, this will be conducted in patients >=12 years of age at baseline.

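### In the readable text, the Week-52 hunger-responder test takes its 10% null from a weight-loss benchmark, so rejecting it does not by itself show a drug effect on hunger

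*SAP*

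**What the plan says.** The Week-52 hunger-responder endpoint is the last of the three key secondary endpoints in SAP 4.3.2. Its test is defined by cross-reference: the proportion based on the "daily hunger score after ~52 weeks of treatment will be analyzed similarly to the primary efficacy endpoint". Protocol 8.5.2.1 does the same and points to Section 8.5.1: "This binary endpoint will be analyzed using the similar statistical method, analysis strategy and" missing-value handling given there.

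Both primary-analysis sections (Protocol 8.5.1, SAP 4.3.1) contain one hypothesis, H0: p ≤ 10%. SAP 4.3.1 explains that this 10% "is the historical reference/control response rate to be statistically compared to the observed response rate in patients treated with setmelanotide". Its source is in the Statistical Considerations of the Protocol synopsis. Among registry patients aged 12 or over, the proportion with at least a 10% "spontaneous weight reduction from the previous 1-year period is approximately 6.4" percent, and 10% was taken as a conservative null.

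Protocol 3.4 treats the two outcomes differently. It rejects a year-long placebo arm "because the projected weight loss responder rate of the untreated population is well understood from the CRIBBS registry". On hunger it says that "the effect of setmelanotide on hunger scores should be rapid and the evaluation strengthened by this initial placebo portion of the study".

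SAP 3.7 adds that "for publication, nominal-p-values will be used to interpret" each key secondary endpoint separately.

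**The concern.** A one-sample test is only as informative as its null. For weight, 10% has a stated empirical basis. For a 25% fall in a self-reported hunger score, the readable text gives no registry, placebo or untreated rate, and 10% has no visible connection to that outcome.

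By Week 52 every patient is on open-label drug, and SAP 4.3.2 accepts a diary week with one completed day in seven. Expectation and diary variation could therefore carry some patients past 25% without a drug effect, and a null borrowed from weight makes no allowance for this. Because the p-value is to be interpreted on its own, a reader may take it as evidence that the drug reduces hunger. It would support only the statement that the responder rate exceeds 10%.

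**Working it through.** **1. The plan's own figure.** The only stated power is for weight: 7 patients, 10% against 66%, giving about 95% at one-sided 0.05 and about 91% at 0.025. The arcsine approximation gives 2(asin√0.66 − asin√0.10)√7 = 3.315. Then Φ(3.315 − 1.645) = 95.3% and Φ(3.315 − 1.960) = 91.2%, so the figures reproduce. They say nothing about hunger, for which the readable text gives neither a null nor a power.

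**2. Inputs for hunger.**
- Null 10%, one-sided 0.025, lower 95% bound above 0.10 (SAP 4.3.1).
- Number analysed: not given. The pivotal cohort is 38 (SAP 1.1.1), and the number aged 12 or over is not in the readable text. Protocol 6.4.5.1 restricts the patient questionnaire to those aged 12 or over who can assess their own hunger. The footnotes to the assessment schedules give the others a caregiver tool instead. Assumed range: n = 16 to 32.
- Untreated rate of at least 25% improvement: not given. Assumed 15%, 20% and 30%, with 10% for reference.

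**3. Rejection rule.** With complete data the 100 imputed datasets are identical, so Rubin pooling reduces to one proportion and its standard error. A Wald-type bound is assumed: k is the smallest count with k/n − 1.96√[(k/n)(1 − k/n)/n] > 0.10.
- n = 16: 6/16 gives 0.375 − 0.237 = 0.138 (reject); 5/16 gives 0.313 − 0.227 = 0.085 (do not reject).
- n = 31: 8/31 gives 0.258 − 0.154 = 0.104 (reject); 7/31 gives 0.226 − 0.147 = 0.079 (do not reject).

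**4. Chance of rejecting with no drug effect,** P(X ≥ k) for X ~ Binomial(n, untreated rate), none missing:

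| n | k | 10% | 15% | 20% | 30% |
|---|---|---|---|---|---|
| 16 | 6 | 0.3% | 2.4% | 8.2% | 34.0% |
| 20 | 7 | 0.2% | 2.2% | 8.7% | 39.2% |
| 28 | 8 | 0.5% | 4.9% | 18.2% | 63.5% |
| 31 | 8 | 1.0% | 8.2% | 27.0% | 75.5% |
| 32 | 9 | 0.3% | 4.1% | 17.5% | 65.6% |
| every n, 16 to 32 | 6–9 | 0.2–1.0% | 2.2–8.2% | 8.2–27.0% | 34.0–75.5% |

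The exact binomial test named in the Protocol, run at 0.025 over the same n, gives 4.2–13.3%, 13.3–35.7% and 46.6–81.2% at 15%, 20% and 30%.

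**5. Missing data.** For values missing for non-administrative reasons, SAP 3.10.2 says "these imputed values will then be replaced with the patient's baseline" value, so those patients count as non-responders. If 20% were missing (assumed), the effective rate is 0.8 times the untreated rate. The Wald-type ranges fall to 0.7–2.7%, 3.0–11.0% and 16.4–47.5%.

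**6. Break-even.** Solving P(X ≥ k) = 2.5% for the untreated rate gives 11.9–15.4% with none missing and, dividing by 0.8, 14.8–19.2% with 20% missing. Below that, the borrowed null does no numerical harm.

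**The case against.** **The carry-over is indirect.** No readable sentence states H0: p ≤ 10% for hunger; both documents say only that the method is similar. A hunger benchmark could stand in parts that cannot be read (Protocol 8.1, unreadable parts of the SAP, a figure missing from SAP 4.3.2). This stands, so the finding is confined to the readable text. If 10% was not meant to apply, the readable text states no null for this test, and the wording still needs attention.

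**The rates are assumed.** Protocol 3.4 calls the hunger unrelenting, and Protocol 1.3 says that non-drug programmes fail, so the untreated rate may be low. This also stands. Nothing readable places the rate above or below the break-even.

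**The lack of a control is a known design feature.** It also affects the Week-52 mean hunger t-test against zero. That is correct: only the borrowed benchmark is peculiar to the responder test.

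**Stronger readings to avoid.** A reader might infer that the trial has no controlled evidence on hunger. SAP 4.3.3 compares mean hunger change with placebo in the blinded 14 weeks, so that is wrong. A reader might infer that the type I error is broken. Against the stated null it is not, since rejection at exactly 10% is 1.0% or less in the table; the fault lies in the benchmark. A reader might quote only the rejection chances of 64–76% at an untreated rate of 30%. Those need about 28–32 self-reporting patients and no missing data, and the restriction on self-report gives reason to doubt that number.

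**Conclusion.** The concern holds as a wrong benchmark in one key secondary test. On the readable text, a significant Week-52 hunger-responder result establishes a rate above 10%, and nothing there ties 10% to what patients would report without the drug. The direction is clear. The size is not: under the assumptions above, it runs from no excess to a rejection probability of about three in four, depending on two quantities that the documents do not give. The primary endpoint is unaffected, and no later key secondary test depends on this one. Severity is minor to moderate.

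**What to change.** Before the primary-analysis snapshot, change SAP 4.3.2 in one of two ways:
- report the Week-52 hunger-responder proportion with its 95% confidence interval and no test against 10%; or
- state a hunger-specific null and justify it.

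The choice of null matters. At an assumed n of 31, the exact test at 0.025 needs 8 responders against 10%, 12 against 20% and 15 against 30%. The interval lets a reader apply any of these.

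Optionally, report the Week-14 responder comparison with placebo as a supportive analysis, counting missing scores as non-response. Protocol 8.5.2.2 plans this comparison, but it is not among the SAP's Week-14 secondary endpoints. SAP 1.1.1 cites a protocol version of 26 August 2020, apparently later than the one supplied, which may have dropped it. Power is low. For an assumed 60% against 20%, an unconditional exact test at one-sided 0.025 has about 28% power with 8 per arm, 42% with 10 and 63% with 16, none missing. The main change does not depend on this.

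The cost is SAP wording and the loss of one easily met p-value in the last-ranked key secondary endpoint. No new data are needed.

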4.3.3. Other Secondary Efficacy Analyses of the 14-week, placebo-controlled period

These analyses will be performed on patients in the PCS population, (i.e., on data from the ~14-week, placebo-controlled, randomized, double-blinded period, or Period 1). Where applicable, the secondary endpoint will be compared against the null hypothesis for each of the 100 imputed datasets. The outcomes from the 100 imputed datasets will be combined using Rubin's Rule to provide a p-value and corresponding confidence interval as appropriate.

Body Weight Percent Change from Baseline at 14 Weeks:

The analysis on this secondary endpoint will be a between-group comparison to investigate if setmelanotide-treated patients (\geq 12 years old) exhibit a greater decrease in percent change in body weight from baseline at \sim 14 weeks of therapy, as compared to placebo-treated patients.

This analysis will be based on a two-sample t-test for each of the 100 imputed datasets. The outcomes from the 100 imputed datasets will be combined using Rubin's Rule to provide a p-value and corresponding confidence intervals. This will be evaluated at a 1-sided, 0.025 significance level.

Sensitivity analyses based on PP at EOP1 and CS may be provided.

Descriptive statistics for the change and percent change from baseline in body weight (kg) may be presented for the PCS population by visit by randomized treatment.

Daily Hunger Score Percent Change from Baseline at 14 Weeks

The analysis on this secondary endpoint will be a between group comparison to investigate if setmelanotide-treated patients exhibit a greater improvement from baseline at ~14 weeks of therapy in weekly average of daily hunger scores, as compared to placebo-treated patients. This analysis will be based on a two-sample t-test for each of the 100 imputed datasets. The outcomes from the 100 imputed datasets will be combined using Rubin's Rule to provide a p-value and corresponding confidence intervals. This will be evaluated at a 1 sided, 0.025 significance level.

Prior to analysis, daily hunger scores for each of the 3 hunger assessments will be averaged separately by week, as outlined above. Sensitivity analyses based on PP at EOP1 and CS may be provided.

Descriptive statistics for the change and percent change from baseline in weekly average of daily hunger scores may be presented based on the PCS population by visit by randomized treatment. Due to the suitability of using the hunger score tool in younger patients, this will be conducted in patients >=12 years of age at baseline.

4.3.4. Sensitivity Efficacy Analyses

Non-Replacement Analysis:

In order to look at the impact of missing weight data on the proportion of patients (\geq 12 years of age) who achieve a \geq 10% reduction in body weight from baseline and percent change from baseline after \sim 52 weeks of treatment, a non-replacement analysis may be done. For the primary analysis and key secondary analyses, patients who have missing 52 week weight data due to nature of study design will utilize the MI imputed 52 week values (described in the above Section 3.10.1) but patients who have missing 52 week data for any other reason will be considered treatment failures (including change and percent change from baseline set to 0). For this sensitivity analysis to be performed on primary and key secondary endpoints, all patients who have missing 52 week data, regardless of the cause, will have their MI imputed 52 week values used and no values will be set to baseline. Similar to the primary and key secondary analyses, this sensitivity analysis will generate 100 imputed datasets as appropriate and the outcomes from the 100 imputed datasets will be combined using Rubin's Rule to provide a p-value and corresponding confidence intervals.

Active Treatment-Completer's Analysis:

In order to look at the impact of missing weight data on the proportion of patients (\geq 12 years of age) who achieve a \geq 10% reduction in body weight from baseline and percent change from baseline after ~52 weeks of treatment, a placebo-completer's analysis may be done. For the primary analysis and key secondary analyses, patients who have missing 52 week weight data due to nature of study design will utilize the MI imputed 52 week values (described in the

above Section 3.10.1) but patients who have missing 52 week data for any other reason will be considered treatment failures (including change and percent change from baseline set to 0). For this sensitivity analysis to be performed on primary and key secondary endpoints, the same data handling will apply, however, placebo-subjects who did not complete 52 weeks of setmelanotide treatment due to the administrative data cut will be excluded. Similar to the primary and key secondary analyses, this sensitivity analysis will generate 100 imputed datasets as appropriate and the outcomes from the 100 imputed datasets will be combined using Rubin's Rule to provide a p-value and corresponding confidence intervals.

[figure not shown]
Daily Hunger:

[figure not shown]
In order to look at the impact of missing hunger data, a sensitivity analysis may be done to examine if there are any differences in conclusions drawn by data availability; analysis for daily hunger scores will be repeated for patients with at least 3 of 7 days of data present. No imputations will be made for missing data.

[figure not shown]
Treatment Failure Analysis:

In order to look at the impact of missing data on the comparisons between setmelanotide-treated patients and placebo patients after ~14 weeks of treatment, a sensitivity failure analysis may be done. For the non-key, secondary endpoints, patients who have missing 14 week data will be considered treatment failures. Similar to the secondary analyses, this sensitivity analysis will be based on a two-sample t-test for each of the 100 imputed datasets. The outcomes from the 100 imputed datasets will be combined using Rubin's Rule to provide a p-value and corresponding confidence intervals.

Statistical Analysis Plan, Protocol RM-493-023 29 October 2020, Version 3.0

Table 3 Summary of Core Analysis Elements

Endpoints	Analysis Set (1) Primary (Sensitivity)	Main Patient Group	Baseline ⁽²⁾	Subgroup Analysis
Primary				
Proportion of patients who achieve a \geq 10% reduction from baseline in body weight after ~52 weeks of treatment	FAS (SH, AG, PP at EOP2)	≥12 years old	ATB	BBS, AS, <12 yo, <17 yo
Key Secondary (after ~52 weeks of treatment)				
Mean percent change from baseline in body weight	FAS (DUS)	≥12 years old	ATB	BBS, AS, <12 yo, <17 yo
Mean percent change from baseline in the weekly average of the daily hunger score	FAS (FAS: 3/7 daily	≥12 years old	ATB	BBS, AS, <12 yo
	responses, DUS)			
Proportion of patients who achieve a $\geq 25\%$ improvement in the weekly average of the daily hunger score	FAS (FAS: 3/7 daily responses)	≥12 years old	ATB	BBS, AS
Secondary (at the Week 14 visit)				
Mean percent change from baseline in body weight after treatment with setmelanotide as compared with placebo	PCS (PP at EOP1, CS)	≥12 years old	PCPB	BBS, AS, <12 yo, <17 yo
Mean percent change from baseline in the weekly average of the daily hunger score after treatment with setmelanotide as compared with placebo	PCS (PP at EOP1, CS, PCS: 3/7 daily responses)	>12 years old	PCPB	BBS, AS, <12 yo

